2.4.2 Secondary Safety Outcome Measures

- Incidence, nature, seriousness, severity and relatedness of all adverse events (AEs), serious adverse events (SAEs) and adverse events of special interest (AESI);
- Infusion related reactions (IRRs) management at each center as per clinical practice;
- Clinical laboratory abnormalities;
- Vital signs.

2.5 OTHER OUTCOME MEASURES

Other variables of interest are below:

- Patient/disease characteristics: age, sex, ECOG PS, Ann Arbor staging, FLIPI (intermediate/high), medical history and history of FL, comorbidities, physical examination and vital signs;
- Treatment pattern:
 - Time from diagnosis to start of treatment with Obinutuzumab;
 - Duration of treatment with Obinutuzumab;
 - Dose modifications;
 - Treatment discontinuation;
 - Prophylaxis medications;
 - Type of chemotherapy chosen in association with Obinutuzumab;
 - Second line regimens prescribed for patients who progressed within two years after starting first line therapy;

- Time to initiation of subsequent systemic anti-lymphoma therapy following initiation of Obinutuzumab containing therapy;
- Adherence to treatments
- Quality of life: EuroQol 5-Dimension Questionnaire, 5-level version (EQ-5D-5L); Functional Assessment of Chronic illness Therapy-Lymphoma (FACT-Lym);
- Presence of B symptoms;
- Concomitant medication prescribed or in current use from the start of therapy with Obinutuzumab until discontinuation of the treatment;
- FDG-PET response at end of induction and end of maintenance, as per clinical practice. When PET is not performed, the alternative routine tumor assessment method will be collected;
- Differences in patient/disease characteristics and treatment pattern/adherence pre- and post- COVID19 pandemic.

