6.5.2 Discontinuation from Treatment with Studied Medicinal Product

The decision for discontinuation from treatment lies with the treating physician in agreement with the patient's decision and is not regulated by this protocol.

The primary reason for early treatment discontinuation should be documented on the appropriate eCRF page. Every effort should be made to obtain information on patients who discontinue treatment.

Patients who discontinue treatment for reasons other than disease progression should continue to have its data collected for radiological assessment and minimal residual disease as collected by clinical practice until disease progression. Data of new anti-cancer therapy within 3.5 years after first line and survival status should also be collected as available.

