6.7.5 Determination of Sample size

Sample size of this clinical study is selected based on feasibility.

Sample size is justified for the primary effectiveness endpoint POD24 treated as binary variable.

A sample size of 300 evaluable patients will allow estimation of the two-sided 95% confidence interval with a width equal to 7.9% (precision 3.95%) of the POD24 when the expected percentage is equal to 13%.

The Clopper-Pearson's formula has been used for the computation.

Table 1 provides the actual width and the precision of the 95% CI and the 95% confidence limits for different percentages of POD24 when the sample size is equal to 300 evaluable patients.

Table 1 - POD24 rate and corresponding 95% Confidence Intervals

POD24 (%)	Actual Width (%)	Precision (%)	95% Clopper-Pearson Exact CI (%)
11%	7.4	3.70	From 7.7 to 15.1
13%	7.9	3.95	From 9.4 to 17.3
15%	8.4	4.20	From 11.2 to 19.6
17%	8.8	4.40	From 12.9 to 21.7

Moreover, a sample size of 300 evaluable patients will allow estimation of the two-sided 95% confidence interval with a width equal to 9.4% (precision 4.70%) of the PFS rate at 3 years (treated as binary variable) when the expected percentage is equal to 80%.

[Table 2](#) provides the actual width and the precision of the 95% CI and the 95% confidence limits for different percentages of PFS at 3 years when the sample size is equal to 300 of evaluable patients.

Table 2 - PFS rate at 3 yrs and corresponding 95% Confidence Intervals

PFS (%)	Actual Width (%)	Precision (%)	95% Clopper-Pearson Exact CI (%)
70%	10.7	5.35	From 64.5 to 75.1
75%	10.1	5.05	From 69.7 to 79.8
80%	9.4	4.70	From 75.0 to 84.4
85%	8.4	4.20	From 80.4 to 88.8
90%	7.1	3.55	From 86.0 to 93.2

Notes: From Gallium trial, PFS at 2 years has been estimated equal to 90% while PFS rate at 3 years to 80%.

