1.2.1 Effectiveness Objectives

The primary effectiveness objective of this study is as follows:

- 1) To evaluate the effectiveness of Obinutuzumab in combination with chemotherapy in previously untreated advanced follicular lymphoma (FL) patients, in the real world setting as measured by the proportion of patients relapsed within 24 months from start of therapy (POD24).

The secondary effectiveness objectives of this study are as follows:

- 2) To evaluate the progression free survival (PFS) at 2 and 3 years;
- 3) To evaluate the overall and complete response rates at mid and end of induction, and during and after maintenance therapy (including the complete response rate at 30 months [CR30]), as per clinical practice, with and without 18F-fluorodeoxyglucose – positron emission tomography (FDG-PET);
- 4) To describe patient/disease characteristics and the second line regimens prescribed for patients who progressed after first line therapy during the overall study duration and within 24 months from start of therapy (POD24);
- 5) To explore the effectiveness of Obinutuzumab in different patient subgroups, stratified by follicular lymphoma International Prognostic Index (FLIPI) – intermediate and high, ECOG performance status (PS), age at study entry, chemotherapy backbone choice, hepatitis infection (history of past/resolved infection or latent HBV after prophylaxis as per standard treatment guidelines), presence of autoimmune disease, history of renal failure and liver failure.

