2.6 DETERMINATION OF SAMPLE SIZE

Sample size of this clinical study is selected based on feasibility.

Sample size is justified for the primary effectiveness endpoint POD24 treated as binary variable. A sample size of 300 evaluable patients will allow estimation of the two-sided 95% confidence interval with a width equal to 7.9% (precision 3.95%) of the POD24 when the expected percentage is equal to 13%.

The Clopper-Pearson's formula has been used for the computation.

Moreover, a sample size of 300 evaluable patients will allow estimation of the two-sided 95% confidence interval with a width equal to 9.4% (precision 4.70%) of the PFS rate at 3 years (treated as binary variable) when the expected percentage is equal to 80%.

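### The second-line regimen variable stops at progression within two years, although the secondary objective it serves covers the whole study, so regimens after later progression would go unreported

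*SAP*

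**What the plan says.** **Objective.** SAP 1.2.1, item 4, and the matching bullet in Protocol 5.2.1 aim to describe patient and disease characteristics and second-line regimens for "patients who progressed after first line therapy during the overall study duration and within 24 months from start of therapy (POD24"). That names two groups: everyone who progresses on study, and the early subset.

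**Variable.** Under treatment pattern, SAP 2.5 and Protocol 6.3.4 both list "Second line regimens prescribed for patients who progressed within two years after starting first line therapy". No other listed variable records which regimen was given. In the same section, the item on patient and disease characteristics has no time restriction.

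**Analysis and outputs.** SAP 3.2.2 contains no analysis of second-line regimens. The effectiveness outputs in SAP Appendix 2 include none for this objective. The nearest entry is a general summary of treatment pattern among the exploratory outputs.

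**Data.** The Protocol synopsis (Study Design) and Protocol Appendix 2 (note b) require follow-up to include new anti-lymphoma therapy, and observation runs to 3.5 years from the start of treatment. Protocol 6.5.2 adds: "Data of new anti-cancer therapy within 3.5 years after first line and survival status should also be collected as available".

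**The concern.** The objective and the variable have different scopes, and the narrower one is an explicit restriction. A programmer working from SAP 2.5 would filter out everyone who progresses after month 24.

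The regimen table would then describe early progressors only. The protocol background (section 4) says these patients have a more aggressive course and receive more lines of therapy, so their second-line treatment may not represent second-line treatment over the study. The early and overall groups named in the objective could not be set side by side. The exploratory objective on treatment pattern in first and second line (SAP 1.2.3, Protocol 5.2.3) has no 24-month limit either.

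**Working it through.** **Inputs**
- 300 evaluable patients (SAP 2.6, Protocol 6.7.5).
- Expected POD24 of 13% and 3-year PFS of 80% (same sections).
- 2-year PFS of 90% (note under Table 2, Protocol 6.7.5).
- Observation of 42 months per patient (SAP 2.1, Protocol 6.1).

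**The plan's own figures.** The documents do not state what share of progressions falls after month 24. What they do state is confidence-interval precision, and it reproduces with exact Clopper-Pearson limits:
- POD24: 39/300 gives 9.41% to 17.34%, width 7.93 points (stated 7.9).
- 3-year PFS: 240/300 gives 75.02% to 84.38%, width 9.36 points (stated 9.4).

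**Share of events after month 24, counted to month 36.** Share = (events by month 36 − events by month 24) / events by month 36.

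1. PFS figures only. Events by month 24: 300 × (1 − 0.90) = 30. By month 36: 300 × (1 − 0.80) = 60. Share = (60 − 30)/60 = 50%.
2. POD24 in place of 2-year PFS. Events by month 24: 300 × 0.13 = 39. Share = (60 − 39)/60 = 21/60 = 35%.
3. As 2, assuming for illustration that 2% of patients die without progression by month 36. Progressions by month 36: 60 − 300 × 0.02 = 54. Share = (54 − 39)/54 = 15/54 = 28%. With 3%, it is (51 − 39)/51 = 12/51 = 24%.

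**Limits of the proxy**
- PFS counts death from any cause. POD24 counts only progression and death due to progression. Calculation 2 therefore treats every death without progression by month 36 as a late progression; calculation 3 shows the effect of removing such deaths.
- Inputs 13% and 90% do not fit together well. Ignoring censoring, 2-year PFS of 90% allows at most 30 events by month 24. If d of these are deaths without progression, which the POD24 analysis excludes, POD24 = (30 − d)/(300 − d), at most 10%. Calculations 1 and 2 are therefore alternative scenarios, not the two ends of one consistent range.
- The objective runs to month 42, but no PFS figure is given beyond month 36. If the month 24–36 rate is assumed to continue, the share by month 42 is 59% (44 of 74) under calculation 1 and 44% (31 of 70) under calculation 2.
- These are counts of events, not of regimens. A patient who progresses late may have no second-line regimen recorded before observation ends.

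**The case against.** The strongest reply is that the objective governs and the variable list is only illustrative. SAP 1.2.3 asks for treatment pattern in first and second line without a time limit, the planned summary of treatment pattern could serve that, and time to next treatment is unrestricted. Output titles in SAP Appendix 2 are generic throughout, so the lack of a named table proves little. SAP Appendix 3, the table templates for the second interim analysis, appears in the available text only as a heading. The analysis is descriptive and no primary estimate depends on it.

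Much of this stands. An analyst who followed the objective would report both groups. It does not remove the mismatch: time to next treatment says when the next therapy began, not what it was, and the one item that does say what it was carries a 24-month limit. Templates for an interim analysis would not settle the scope of the final one.

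A reader might also infer that the study cannot answer this objective, or that a third to a half of progressions would go undescribed. The documents support neither. New anti-lymphoma therapy is collected in follow-up, and late progressors can be characterised because that item has no time limit. The PFS figures alone give one half; the third needs the POD24 assumption, mixes two event definitions, and is not a lower bound. One caution runs the other way: the documents do not show how much regimen detail the eCRF records. In addition, the Protocol 6.5.2 sentence follows one about patients who stop treatment for reasons other than progression, so the synopsis and Appendix 2 are the better support for data collection.

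**Conclusion.** The mismatch is real and appears in the current text of both documents. Followed as written, the plan would not report the second-line regimens of patients who progress between months 24 and 42, which a stated secondary objective requires. The gap is confined to regimens and lies in the definition of the variable and its output, not in the planned follow-up.

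Its size can only be approximated. About 50% of PFS events by month 36 fall after month 24 on the protocol's PFS figures, 35% with POD24 of 13%, and about 28% if 2% of patients are also assumed to die without progression. The number of affected regimens is smaller than the event counts suggest, by an amount the documents do not allow us to estimate. The primary endpoint, the sample size and the other secondary endpoints are unaffected. It should still be corrected, because the content of the table should not depend on which of two sentences the analyst follows.

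**What to change.** - In SAP 2.5 and Protocol 6.3.4, define the variable as second-line regimens for all patients who progressed after first line during the 42-month observation period, shown overall and split by progression within 24 months versus later.
- Show patient and disease characteristics by the same split.
- Name this table in SAP Appendix 2 as the output for the objective numbered 4 in SAP 1.2.1.

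The cost is a wording change in both documents and one extra descriptive table. No new follow-up is needed, since new anti-lymphoma therapy is already collected to 3.5 years. It is worth confirming that the eCRF field records the regimen as well as its start date.

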2.6 DETERMINATION OF SAMPLE SIZE

Sample size of this clinical study is selected based on feasibility.

Sample size is justified for the primary effectiveness endpoint POD24 treated as binary variable. A sample size of 300 evaluable patients will allow estimation of the two-sided 95% confidence interval with a width equal to 7.9% (precision 3.95%) of the POD24 when the expected percentage is equal to 13%.

The Clopper-Pearson's formula has been used for the computation.

Moreover, a sample size of 300 evaluable patients will allow estimation of the two-sided 95% confidence interval with a width equal to 9.4% (precision 4.70%) of the PFS rate at 3 years (treated as binary variable) when the expected percentage is equal to 80%.

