6.1.3 Number of Patients Observed in the Study

Approximately 300 patients will take part in this study.

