6.8.5 Administrative Structure

This trial will be sponsored and managed by Roche S.p.A. The Sponsor will provide clinical operations management, data management, and medical monitoring.

Approximately 50 sites in Italy will participate to enrol approximately 300 patients. Enrolment will be competitive across sites.

Enrolment will occur through an ~~eCRF interactive web-response system (IWRs)~~ or similar system to capture electronically enrolled patients.

~~Accredited~~ Local laboratories will be used for routine monitoring; local laboratory ranges will be *included in eCRF* collected as applicable.

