2.3 PRIMARY OUTCOME MEASURES

Progression of disease at 2 years (POD24), defined as the time from the date of treatment initiation with Obinutuzumab until the first documented progression of disease

or death due to disease progression, whichever occurs first, within 24 months from the start of treatment with Obinutuzumab. Patients who have no disease progression and have not died due to disease progression or who are lost to follow-up at the time of analysis will be censored at the date of last tumor assessment where no progression was documented or the last date of follow-up for disease, whichever is last. Patients without post-baseline tumor assessments will be censored at the time of their baseline visit unless death due to disease progression occurs prior to their first scheduled tumor assessment. Patients who die for reasons not related to the disease progression within 24 months from the treatment start with Obinutuzumab will be excluded from the statistical analysis of the endpoint.

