3. STATISTICAL METHODS

The statistical analysis will be performed using the R Statistical Software (Foundation for Statistical Computing, Vienna, Austria) version 3.6.0 or higher.

This is not a hypothesis testing study but an exploratory study with predefined precision of estimates for key efficacy and safety parameters; there are no formal statistical hypotheses tests to be tested, and there will be no adjustments for multiplicity of endpoints or within-subgroups comparisons.

Data will be summarized using appropriate descriptive statistics. Categorical data will be presented as frequencies and percentages. For continuous data, arithmetic mean, standard deviation (SD), median, interquartile range (IQR), minimum, and maximum will be presented. The 95% confidence interval of the observed proportions (calculated using either the Clopper-Pearson methodology, or the Poisson distribution, for frequencies below 10%) will be provided.

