3.1 ANALYSIS POPULATIONS

The following populations will be considered for data analysis:

Effectiveness population

Effectiveness analysis population includes all patients who are enrolled and have received at least two cycles of Obinutuzumab.

Safety population

Safety analysis population includes all patients who are enrolled.

Screening failures are not considered for the analyses.

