3.2.1 Primary Outcome Measures

The primary endpoint is progression of disease at 2 years (POD24).

POD24 will be analyzed according to the survival analysis methods. The quartiles with their 95% confidence interval (estimated using Kaplan-Meier methods and Greenwood's formula) will be presented. Kaplan-Meier plots with a 95% CI will be prepared. Estimates for the survivor function will be obtained by the Kaplan-Meier approach.

Moreover, the POD24 will be analyzed as binary variable. Number and percentage of patients with its 95% CI for POD24 will be calculated.

Logistic regression analysis will be performed to assess which variables are predictive of POD24. To identify factors associated with POD24, logistic regression analysis will be performed with backwards selection (removing factors with $P > 0.05$). Univariable associations between factors and POD24 will be calculated by using the Chi-square test.

In the analysis of POD24 will be excluded patients who die within 24 months from the treatment start with Obinutuzumab for reasons not related to the disease progression.

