3.6 HANDLING OF MISSING DATA

There will be no missing value handling mechanisms and missing data will not be imputed.

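### The planned CI widths assume 300 evaluable patients although only about 300 are enrolled, and binary POD24 has no rule for patients lost event-free before 24 months

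*SAP*

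**What the plan says.** **Precision.** SAP 2.6 and protocol 6.7.5 choose the sample size on feasibility and justify it by the precision of POD24 as a yes/no variable: "A sample size of 300 evaluable patients will allow estimation of the two-sided 95% confidence interval with a width equal to 7.9% (precision 3.95" percent, when 13% is expected. A second statement gives a width of 9.4 points for three-year PFS at 80%. The method is Clopper-Pearson.

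**Enrolment.** Protocol 6.1.3: "Approximately 300 patients will take part in this study". Protocol 6.8.5: "Approximately 50 sites in Italy will participate to enrol approximately 300 patients". Protocol 6.5.3 does not replace withdrawals. Protocol 6.4.2 does not treat a missing tumour assessment as a deviation. No expected loss is given, and evaluable is not defined.

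**Endpoint.** SAP 2.3 defines POD24 as a time from treatment start, with censoring for patients who are event-free or lost. It adds: "Patients who die for reasons not related to the disease progression within 24 months from the treatment start with Obinutuzumab will be excluded". SAP 3.2.1 plans Kaplan-Meier quartiles, plots and the survivor function, and then: "Moreover, the POD24 will be analyzed as binary variable. Number and percentage of patients with its 95% CI for POD24 will be calculated". The population, in SAP 3.1, is: "Effectiveness analysis population includes all patients who are enrolled and have received at least two cycles of Obinutuzumab". On missing data, SAP 3.6 says: "There will be no missing value handling mechanisms and missing data will not be imputed". SAP 3.4 plans no sensitivity analyses.

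**Time origin.** SAP 3.2 measures time-to-event endpoints in general from enrolment, whereas SAP 2.3 measures POD24 from the start of obinutuzumab.

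**The concern.** Two things do not fit together.

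First, the width is quoted for 300 evaluable patients, and 300 is also roughly the whole enrolment. Withdrawal, loss to follow-up and other-cause death can only reduce that number. SAP 3 describes the study as one with precision fixed in advance, so a reader will take 7.9 and 9.4 points as the widths to expect.

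Second, censoring tells a Kaplan-Meier analysis what to do with a patient lost at month 15 without progression. It does not say whether that patient is a yes, a no, or absent from a percentage. Using the SAP 3.1 population as denominator makes the patient a non-event and pushes the percentage down. Reading SAP 3.6 as leaving the patient out pushes it up. Nor does the text say whether a clear scan at month 22, inside the 22-26 month window of protocol 6.4.2, establishes the 24-month status. One data set can therefore give two primary percentages, and the choice could be made after the data are seen.

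The same gap affects the second interim (SAP 3.8), about two years after the first patient enters. Consent falls within a year of treatment start, so anyone enrolled in the 12 months before that cut has under 24 months of observation.

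**Working it through.** **1. The plan's own figures.** For x events in n, the limits are the 2.5% quantile of Beta(x, n-x+1) and the 97.5% quantile of Beta(x+1, n-x).
- POD24, 39/300: 9.41 to 17.34, width 7.93 (plan: 9.4 to 17.3, 7.9).
- Three-year PFS, 240/300: 75.02 to 84.38, width 9.36 (plan: 75.0 to 84.4, 9.4).

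Both reproduce, as do the other rows of protocol Tables 1 and 2.

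**2. Widths with fewer evaluable patients.** Enrolment 300; the loss is assumed; x = p × n, not rounded.

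| Loss | n | POD24 at 13% | PFS at 80% |
|---|---|---|---|
| 0 | 300 | 7.9 | 9.4 |
| 5% | 285 | 8.1 | 9.6 |
| 10% | 270 | 8.4 | 9.9 |
| 15% | 255 | 8.6 | 10.2 |
| 20% | 240 | 8.9 | 10.5 |

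For PFS only withdrawal and loss count, because every death is an event.

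**3. The two readings of binary POD24.** Assume a true 24-month rate of 13%, constant hazards and non-informative loss. The event hazard is h = -ln(0.87)/24 = 0.00580 per month. The loss hazard c is set so that a share L is lost event-free before month 24.

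*Loss starting at treatment start.* Observed event share = h/(c+h) × (1 - exp(-24(c+h))). At L = 10%, c = 0.00471, so the share is 0.5517 × 0.2231 = 12.3%. That is the percentage with lost patients as non-events. Leaving them out divides by 1 - L: 12.3/0.9 = 13.7%.

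*Loss starting at study entry.* Consent follows at least two cycles and comes within a year of treatment start, so I also let entry month e be uniform over 2-12 (assumed), with progression before entry still counted. The event share is the average over e of 1 - exp(-he) + exp(-he) × h/(c+h) × (1 - exp(-(24-e)(c+h))), with c re-solved. At L = 10%, c = 0.00681, giving 12.5%, and 12.5/0.9 = 13.9%.

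| L | From treatment start: non-events / left out / gap | From entry: non-events / left out / gap |
|---|---|---|
| 5% | 12.7 / 13.3 / 0.7 | 12.7 / 13.4 / 0.7 |
| 10% | 12.3 / 13.7 / 1.4 | 12.5 / 13.9 / 1.4 |
| 15% | 12.0 / 14.1 / 2.1 | 12.2 / 14.4 / 2.2 |
| 20% | 11.6 / 14.5 / 2.9 | 12.0 / 15.0 / 3.0 |

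The timing of loss changes how the error divides around 13%; the gap hardly moves.

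**4. Kaplan-Meier at 24 months.** The large-sample Greenwood variance is S² × h × (exp(24(c+h)) - 1)/((c+h) × 300), with S = 0.87 and loss from treatment start. At L = 10%: 0.7569 × 0.00580 × 27.3/300 = 0.000400, SE 0.0200, width 2 × 1.96 × 0.0200 = 7.8 points. The widths for 0, 5 and 20% loss are 7.6, 7.7 and 8.1. This leaves out delayed entry and the exclusion of other-cause deaths.

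**The case against.** - **The precision statement is conditional and true.** It says evaluable, the sample size is declared feasibility-based, and nothing is tested. Protocol Table 1 already shows widths from 7.4 to 8.8 for rates of 11-17%, and the 8.4 at 10% loss equals its 15% row. Follow-up to 42 months regardless of discontinuation, with contact every 3-6 months, limits the loss. All of this stands, and it makes the first part a reporting correction.
- **Kaplan-Meier is named first and keeps censored patients.** This also stands. But SAP 2.6 rests the sample size on the binary version, and SAP 3.2.1 names no 24-month Kaplan-Meier estimate.
- **PFS is scheduled only as Kaplan-Meier in SAP 3.2.2.** Correct: the wider PFS figures restate a planning number, not a scheduled output.
- **Loss cannot begin at month 0.** Correct, because consent follows at least two cycles. A bound that places all loss at treatment start is unattainable. That is why loss from entry is shown beside loss from treatment start.

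A reader might infer that the study is too small. The documents do not support this: no target width or test is missed, and the widening is 0.2-1.1 points across the assumed range.

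**Conclusion.** The stated widths are correct for 300 evaluable patients and somewhat better than an enrolment of about 300 should deliver. That part is modest, and its size rests on an assumed 5-20% loss.

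The missing status rule matters more, because it moves the primary percentage itself. At 10% loss and a true 13%, the result is low by about 0.5-0.7 points if lost patients are non-events, and high by about 0.7-0.9 if they are left out. At 20% loss the figures are about 1.0-1.4 and 1.5-2.0, and the gap of about 3 points approaches the planned half-width of 3.95. These sizes assume constant hazards and non-informative loss. That no rule exists rests on no assumption.

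A reader might also infer that 13% is wrong, because protocol 6.7.5 notes 90% two-year PFS in the earlier trial. That would cap POD24 at about 10% only if both figures described the same population, which the documents do not show. A lower rate would in any case narrow the interval (7.1 points at 10%, n = 300).

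The text should be changed; the design stands.

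**What to change.** 1. **SAP 2.6, protocol 6.7.5 and synopsis.** Keep enrolment at about 300. State an assumed evaluable number and give its POD24 and PFS widths beside those for 300.
2. **SAP 2.3 and 3.2.1.** Make the lead estimate the Kaplan-Meier cumulative incidence of POD24 at 24 months from treatment start, with its 95% CI. Bring the time origin in SAP 3.2 (enrolment) into line with SAP 2.3 (treatment start). Otherwise 24 months could mean points up to a year apart.
3. **Binary POD24.** Report it as supportive, limited to patients with progression or death due to progression within 24 months, or documented progression-free at or after a stated month. Say whether a scan at months 22-24 qualifies. Do not count patients lost early as non-events.
4. **Limits to state.** Kaplan-Meier assumes non-informative loss. Entry after treatment start and the exclusion of other-cause deaths limit its interpretation.
5. **Minor wording.** Name Clopper-Pearson for binary POD24, since SAP 3 allows intervals "calculated using either the Clopper-Pearson methodology, or the Poisson distribution, for frequencies below 10" percent. Give the source of the 13%.

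The cost is text and one output line, with no added patients. Restoring 300 evaluable would take 316 enrolled at 5% loss (300/0.95) up to 375 at 20% (300/0.80), which is not needed in a feasibility-sized study. The quoted widths become 0.2-1.1 points less favourable, and the supportive percentage keeps its upward bias, which is why it should not lead.
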